6.5 CONCOMITANT THERAPY

Participants will be permitted to continue any other OA treatment during the course of the study.

7 STUDY INTERVENTION/ DISCONTINUATION AND PARTICIPANT DISCONTINUATION/WITHDRAWAL

7.1 DISCONTINUATION OF STUDY INTERVENTION

When a participant discontinues the *OA CARE* intervention, they will be asked if they are willing to continue with other remaining activities (e.g., follow-up assessments) based on the study protocol. If a clinically significant finding is identified after enrollment (e.g. health-related changes that may change the safety level of participation), the investigator or qualified designee will determine if any change in participant management is needed. Any new clinically relevant finding will be reported as an adverse event (AE). The data to be collected at the time of study intervention discontinuation will include the reason(s) for discontinuing the participant from the intervention, and methods for determining the need to discontinue.

7.2 PARTICIPANT DISCONTINUATION/WITHDRAWAL FROM THE STUDY

Participants are free to withdraw from participation in the study at any time upon request. An investigator may discontinue a participant from the study for the following reasons:

- Lost-to-follow up; unable to contact subject
- Any event or medical condition or situation occurs such that continued collection of follow-up study data would not be in the best interest of the participant or might require an additional treatment that would confound the interpretation of the study
- The participant meets an exclusion criterion (either newly developed or not previously recognized) that precludes further study participation

The reason for participant discontinuation or withdrawal from the study will be recorded in the study database. Participants who discontinue or are withdrawn will be replaced up to the point of randomization assignment being given to the participant. Once participants are given their randomization assignment, they will be counted toward the total study sample size and not replaced.

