4.2 SCIENTIFIC RATIONALE FOR STUDY DESIGN

Although this exploratory trial is not designed with statistical power to test the efficacy of OA CARE, we have included a UC group (rather than conducting a single-group study) for several reasons. First, this provides an opportunity to assess acceptability of randomization to a UC group, from the patient perspective. Second, we will be able to evaluate follow-up rates for both groups, which will inform potential adaptations and sample size estimation for a larger trial. Third, this will provide a better preliminary assessment of the efficacy of OA CARE (Aim 2) than a single group pre-post trial, since improvement is consistently observed in control groups within OA trials ^{22,29,31,38}. We have specifically selected a UC control group (versus an attention control condition) because our ultimate goal is to test how well OA CARE performs relative to the typical care patients receive for OA. Assessments for this trial will be conducted at baseline, 6-months (corresponding to the beginning of the second phase of OA CARE), and 12-months (intervention completion).

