4.4 END-OF-STUDY DEFINITION

A participant is considered to have completed the study if he or she has completed 12-month follow-up assessment.

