7.3 LOST TO FOLLOW-UP

A participant will be considered lost to follow-up if he or she fails to return for the final, 12-month follow-up assessment. If a participant misses intervention calls or follow-up assessments prior to the 12-month time point and cannot be contacted during the time frame, the study team will still attempt to contact the participant for remaining calls / assessments. The study team must attempt to contact a participant at least 3 times, on different days of the week, different times of day, and across at least 2 weeks, before they are considered to have missed a visit / assessment or be lost to follow-up. These contact attempts will be documented in the study database.

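### Section 7.2 lets an investigator end a randomised participant's study participation over a possibly confounding treatment or a precluding exclusion criterion, and no supplied text says the 6- and 12-month outcomes are still sought

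*Combined protocol and SAP*

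**What the plan says.** Section 7.2 lists reasons for which an investigator may discontinue a participant from the study. Two matter here. The first is an event, condition or situation that "might require an additional treatment that would confound the interpretation of the study". The same bullet also covers the participant's best interest, which is a separate reason and is not questioned here. The second reads: "The participant meets an exclusion criterion (either newly developed or not previously recognized) that precludes further study participation".

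The section reaches randomised participants: anyone told their assignment still counts in the 60 and is not replaced. The stated follow-through is a record: "The reason for participant discontinuation or withdrawal from the study will be recorded in the study database".

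Three nearby rules bear on this.

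- **7.1** deals with people who stop OA CARE: "they will be asked if they are willing to continue with other remaining activities (e.g., follow-up assessments").
- **7.3** deals with people who miss contacts and cannot be reached: "the study team will still attempt to contact the participant for remaining calls / assessments".
- **6.5** says "Participants will be permitted to continue any other OA treatment during the course of the study".

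Sections 9.3 and 9.4 plan an intent-to-treat analysis. It is a mixed model on the available follow-up data, with baseline WOMAC as a covariate, valid under MAR. Multiple imputation is planned if missing data are extensive and judged not MAR.

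**The concern.** Section 4.2 explains the choice of control group: "our ultimate goal is to test how well OA CARE performs relative to the typical care patients receive for OA". Treatments that patients come to need over a year are part of such care. Ending someone's participation because such a treatment might be needed takes out of the data what the comparison is meant to include. The plan does not define which treatments would confound a comparison with usual care. Section 6.5 does not settle it, since permission to continue other treatment may not cover starting one. OA CARE itself leads to new referrals after 6 months (6.1), so the word could be read differently in the two arms.

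An exclusion criterion can also arise through worsening disease. A planned joint replacement is on the list in 5.2. If an investigator judged that it precluded participation, the lost outcome would probably be related to the reason for the loss.

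Two uses of the data are affected. One is the between-group contrast, which is to inform the larger trial's sample size. The other is the follow-up completion rate, a feasibility metric (8.1) that 4.2 also wants for planning. Under 4.4, "A participant is considered to have completed the study if he or she has completed 12-month follow-up assessment", so a removed participant cannot count as a completer.

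**Working it through.** **1. Does any text close the gap?** Section 7.1's follow-up offer is triggered by stopping OA CARE, so by its wording it does not reach usual-care participants or removals under 7.2. Section 7.3 is triggered by missed contacts. Section 8.1 gives the general schedule without mentioning discontinued participants. Intent-to-treat in 9.3 and 9.4 governs analysis and does not create data. Because baseline WOMAC is a covariate, someone removed before 6 months has no outcome record in the model. The Manual of Procedures was not available.

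**2. The plan's own precision figure.** Section 9.2 claims more than 80% power at 1.7 SD with 30 per arm, two-sided 0.05, allowing for clustering in the OA CARE arm. It gives no intraclass correlation (ICC), so the figure cannot be reproduced from stated inputs. With groups of 10 and SE = sqrt([1 + 9 x ICC]/30 + 1/30):

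- ICC 0: the 80%-power effect is 0.72 SD.
- ICC 1: SE = sqrt(11/30) = 0.606, and 2.80 x 0.606 = 1.70 SD (power 80.2%).
- A t test on 2 df: 1.62 SD at ICC 0.05 and 1.76 SD at ICC 0.10.

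It serves here only as a yardstick. The implied SE is 1.7/(1.96 + 0.84) = 0.607, so the 95% half-width is 1.96 x 0.607 = 1.19 SD. The 2-df reading gives 4.303 x sqrt(2.45/30) = 1.23 SD to 4.303 x sqrt(2.90/30) = 1.34 SD. Without clustering and with baseline adjustment, it is t(57) x sqrt(2/30) x sqrt(1 - r^2) = 0.448 SD (r = 0.5) or 0.369 SD (r = 0.7).

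**3. Size of the shift (all inputs assumed).** Shares removed are 4/30 and 1/30. Removed patients are g = 0.5 to 1 SD worse at 12 months than those retained. Correlation r between any two visits is 0.5 to 0.7, and the true effect is 0. Removal depends on 12-month WOMAC. Then, approximately:

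shift = (4/30 - 1/30) x g x (1 - R^2)

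R^2 is the share of 12-month variance explained by what was observed before removal: r^2 if only baseline, 2r^2/(1 + r) if baseline and 6 months.

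| Removed | r | 1 - R^2 | g = 0.5: formula (simulated) | g = 1: formula (simulated) |
|---|---|---|---|---|
| before 6 months | 0.5 | 0.750 | 0.038 (0.037) | 0.075 (0.076) |
| before 6 months | 0.7 | 0.510 | 0.026 (0.025) | 0.051 (0.053) |
| after 6 months | 0.5 | 0.667 | 0.033 (0.033) | 0.067 (0.068) |
| after 6 months | 0.7 | 0.424 | 0.021 (0.021) | 0.042 (0.043) |

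The simulation used 400,000 per arm and the planned type of model (random intercept, baseline covariate, group by time), without clustering. The shift favours the arm with more removals. Its range, 0.021 to 0.076 SD, is 6% (0.021/0.369) to 17% (0.076/0.448) of the unclustered half-width, and about 2% to 6% of 1.19 SD.

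In milder cases:

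- 2 vs 1 removed: 0.01 to 0.03 SD.
- Equal removals (3 vs 3) with no true effect: within 0.002 of 0.
- Removal driven only by the observed 6-month WOMAC: within 0.002 of 0.
- 4 vs 1 with outcomes obtained from half of those removed: 0.009 to 0.035 SD.

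Lost power is a lesser matter: removing 5% to 20% per arm moves the unclustered 80%-power effect from 0.72 to 0.74-0.81 SD.

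**4. Completion rate.** One removal is 1/30 = 3.3 points in its arm and 1/60 = 1.7 points overall. With 4 vs 1, if all others complete, the rates are 26/30 = 86.7% and 29/30 = 96.7%, a gap of 10 points. If only half of those removed could have been followed, the avoidable part is 2/30 - 0.5/30 = 5 points.

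**The case against.** The power in 7.2 is discretionary, and the exclusion ground is limited to criteria that preclude participation. Some of those criteria, such as psychosis or significant cognitive impairment, may make valid questionnaires impossible. That stands, and the change needs an exception for it. Section 7.1 also asks for case-by-case judgement on clinically significant findings after enrolment in either arm, but it speaks of participant management and is silent on outcomes. An exclusion missed at enrolment may be handled as a protocol deviation under the Manual of Procedures, which could not be checked.

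The trial is exploratory and 4.2 says it is not powered for efficacy. The non-zero shifts need both unequal removals and removal tied to unobserved outcome. That also stands, and it keeps the point small.

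Four stronger readings are tempting, and the documents do not support them:

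- **The pilot's contrast will be materially biased.** No removal rates are given, and even the adverse case is a small fraction of the interval width.
- **Investigator decisions alone would open a 10-point completion gap.** That figure restates the assumed 4 vs 1 and presumes that all five would otherwise have completed.
- **The plan has no answer to data that are not MAR.** Multiple imputation is named, though only for extensive missingness, which a few removals may not amount to.
- **Removed participants leave the analysis.** They still count in the sample, and nothing says that collected data are deleted.

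Separate tabulation of investigator-initiated removals is a reporting choice that the recorded reasons already permit.

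**Conclusion.** The point holds in a limited form. Section 7.2 contains a stated rule that can end outcome collection after randomisation on grounds that may be related to outcome or may differ by arm. Within the supplied documents nothing offsets it, and it conflicts with an intent-to-treat comparison against typical care. The direction and size of any bias are unknown. On the assumptions above the 12-month contrast moves by about 0.02 to 0.08 SD at worst and by about nothing in the benign cases. The feasibility effect is 3.3 points of arm completion per avoidable removal; under 4 vs 1 the gap is at most 10 points, or about 5 if half could be followed. The case for change rests on low cost and on the value of clean follow-up rates for the next trial, not on a threat to this pilot's result.

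**What to change.** Reconcile 7.1, 7.2 and 9.3. After randomisation, in either arm, a possibly confounding treatment or a newly met exclusion criterion should not by itself be a ground for ending outcome collection. Keep seeking the scheduled 6- and 12-month outcomes, at least the WOMAC. Section 8.1 already has the 6-month measures done by phone and allows the 12-month questionnaires to be. The exceptions are that the participant withdraws, cannot validly take part, or collection is not in their best interest (already in 7.2). Record the event and its date, and include the data in the intent-to-treat analysis. Decisions on stopping the intervention are unchanged.

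The cost is a short amendment with any IRB or consent update, modest staff time for contacts that are already scheduled, and participant payments of at most USD 40 + USD 60 = USD 100 per affected person (8.1), so about USD 500 for five.

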5.5. STRATEGIES FOR RECRUITMENT AND RETENTION

We will recruit patients from UNC Health. In particular, we will partner with the UNC Internal Medicine Clinic and UNC Family Medicine, which serves high proportions of patients who are African American and non-white Hispanic, as well as uninsured patients. This is important because of disparities in OA among these demographic groups⁴⁵, and our aim for *OA CARE* to particularly reach the most vulnerable patients. Our team has a strong track record of recruiting African American and non-White Hispanic patients^{28,31,46}. Our main recruitment method will mirror the process by which we envision *OA CARE* will ultimately function in clinical settings. Specifically, PCPs will be asked to refer patients to *OA CARE*. This may occur via the EHR or another UNC approved method of transferring PHI. A study team member will then screen the EHR for potential exclusion criteria and contact the patient to assess interest and administer a brief screening questionnaire. If needed, we will also identify potential participants via an EHR data pull, then send introductory letters and follow up with a screening phone call. However, a key goal for this exploratory study is to develop procedures to maximize provider referrals, as this will be critical for downstream implementation. All eligible patients will be asked to attend a baseline visit that will involve completion of consent, baseline assessments and receipt of an accelerometer. Following return of the accelerometer, participants will be informed of their randomization assignment via telephone. A participant will be considered enrolled once they have consented and been randomized.

To facilitate completion of recruitment calls, as well as baseline and follow-up assessment calls, we will call participants on different times of day and different days, across multiple weeks. We have used this strategy successfully in prior studies to reach participants at times convenient to them.

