6.3 MEASURES TO MINIMIZE BIAS: RANDOMIZATION AND BLINDING

The randomization scheme will be generated by the study statistician and stored within the study database. The database will be configured so that blinded study personnel (e.g., those conducting follow-up assessments) will not have access to randomization information. The participants will not be notified of randomization assignment until all baseline assessments are complete. In addition, an individual participant's randomization assignment will not be known to any study personnel until baseline assessments are complete.

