9.3 POPULATIONS FOR ANALYSES

The primary analyses will be conducted using an intent-to-treat approach. Supportive exploratory analyses may be conducted to consider samples with greater completion of study intervention visits. Since this is an exploratory trial, the nature of these supportive analyses will be based on observed patterns of intervention contacts.

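### Section 7.2 allows a randomised participant to be replaced until told the assignment, at a time when unblinded staff could already know it

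*Combined protocol and SAP*

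**What the plan says.** Five sections bear on when a person becomes part of the trial sample.

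- **Section 7.2 (replacement and counting).** "Participants who discontinue or are withdrawn will be replaced up to the point of randomization assignment being given to the participant". It continues: "Once participants are given their randomization assignment, they will be counted toward the total study sample size and not replaced". The section also lists grounds on which an investigator may discontinue someone. These include being unable to reach the person and finding an exclusion criterion that is new or had been missed. The reason must be recorded.
- **Section 5.5 (enrolment and notification).** "A participant will be considered enrolled once they have consented and been randomized". On the order of events: "Following return of the accelerometer, participants will be informed of their randomization assignment via telephone".
- **Section 6.3 (concealment).** An individual's "randomization assignment will not be known to any study personnel until baseline assessments are complete". After that point the only stated bar is on blinded staff: "The database will be configured so that blinded study personnel (e.g., those conducting follow-up assessments) will not have access to randomization information".
- **Sections 9.3 and 9.4 (analysis set).** "The primary analyses will be conducted using an intent-to-treat approach". Section 9.4 repeats the commitment. Neither section says which participants make up the set.

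**The concern.** Two events are used as the point of no return. Section 5.5 uses randomisation, and Section 7.2 uses the participant being told. Anyone between the two is enrolled under one section but uncounted and replaceable under the other.

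This matters because of what staff may know in that interval. Once baseline is complete, nothing bars unblinded staff from seeing the assignment, and nothing says they learn it no earlier than the participant. Decisions made then could depend on the arm: how hard to pursue someone by telephone, or whether a health condition is a reason to exclude. Section 5.2 leaves one exclusion criterion to the study team's judgement. Removing people after allocation, with the allocation visible, is a recognised route to selection bias.

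There is also a cost to the pilot's own purpose. Section 4.2 justifies the usual-care arm partly by the wish to measure follow-up rates in both groups, and Section 9.2 says the drop-out seen will inform the larger trial's sample size. Randomised people who are replaced and not counted drop out of those denominators.

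**Working it through.** The plan gives no figure for participants replaced after randomisation, so there is none to reproduce. The power statement in Section 9.2 does not depend on this point. The check is mainly a reading of the rules side by side.

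**1. Status of one participant at each stage**

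| Stage | Section 5.5 | Section 7.2 | Who may know the arm (6.3) |
|---|---|---|---|
| A. Consented, not randomised | Not enrolled | Replaceable, not counted | No one, as nothing is assigned |
| B. Randomised, baseline not complete | Enrolled | Replaceable, not counted | No study personnel |
| C. Randomised, baseline complete, not yet told | Enrolled | Replaceable, not counted | Unblinded staff are not barred |
| D. Told the assignment | Enrolled | Counted, not replaced | Unblinded staff and the participant |

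Sections 5.5 and 7.2 agree at A and D and disagree at B and C. At B the allocation is concealed, so a withdrawal cannot depend on the arm. Only C carries the bias route.

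**2. Can anyone be in stage C?** The documents do not say when an individual's assignment is drawn relative to the call. If it is drawn before the call, stage C lasts until the participant is reached. Section 7.3 requires at least 3 contact attempts over at least 2 weeks before someone is treated as having missed an assessment or as lost. If that rule also governed the notification call, which is not stated, a hard-to-reach person could remain in stage C for 2 weeks or more. If the assignment is drawn during the call, stage C almost disappears.

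**3. Size, on assumed values**

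Inputs: 60 counted participants, 30 per arm (Section 9.2). Assumed: k people replaced, and a mean difference of g SD between those removed and their replacements. The documents give neither.

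- Share of those randomised who are replaced: k / (60 + k). For k = 1, 1/61 = 1.6%. For k = 2, 2/62 = 3.2%. For k = 3, 3/63 = 4.8%. The denominator is 60 + k because replacement brings the counted total back to 60.
- Shift in one arm's mean if all k fall in that arm: (k/30) × g. The smallest case is (1/30) × 0.25 = 0.008 SD. The largest, with k = 3, is (3/30) × 1.0 = 0.10 SD. A more extreme case, k = 5 and g = 1.0, gives 5/65 = 7.7% replaced and a shift of (5/30) × 1.0 = 0.167 SD.
- For scale, the standard error of a difference between two arms of 30, ignoring clustering and baseline adjustment, is √(1/30 + 1/30) = 0.258 SD. A shift of 0.10 SD is about 0.4 of that (0.10/0.258 = 0.39).

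**4. After the change.** Counting from randomisation leaves the target at 60 under the Section 5.5 definition. No input to the sample size statement moves.

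**The case against.** The strongest reply is that stage C may be empty. Section 6.3 uses the same milestone, completed baseline assessments, for both staff and participants, and Section 5.5 places the call after the accelerometer comes back. Accelerometry is a baseline measure, so its return may itself complete baseline, and staff access and notification may open together. Section 5.4 also defines screen failures as people who consent but are not then assigned or entered. Read with that, Section 7.2 could be the ordinary rule that losses between consent and assignment are replaced. The schema that might settle the timing is not reproduced in the text available, and the schedule of activities is too badly aligned there to rely on.

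What stands is that the length of the window is not established and may be close to nil. The reply does not remove the point, because Section 7.2 fixes the cut-off at the participant being told. A common milestone sets only the earliest time for both events, and a call that fails leaves the participant untold while unblinded staff may know.

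A reader might go further in three ways that the documents do not support.

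- *That the rule contradicts intent-to-treat.* Section 7.2 governs replacement and counting. It does not define the analysis set, and Sections 9.3 and 9.4 do not exclude a randomised, un-notified person. The set is undefined, which is a gap and not a contradiction.
- *That replacement upsets the 10:10 split within blocks of 20.* Section 4.1 gives the block size, but no section says whether a replacement takes the vacated slot, which would keep the balance, or the next one.
- *That staff do see the allocation and drop people because of it.* The text leaves this possible and says no more. Recorded withdrawal reasons would also make any such case traceable.

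**Conclusion.** The concern holds as a defect in the rule. Sections 5.5 and 7.2 disagree on when a randomised person belongs to the trial, and Section 7.2 as written allows someone to be replaced after randomisation when unblinded staff could know the arm. That the person would then be missing from the analysis is an inference from the undefined intent-to-treat set.

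The likely effect is small. With an assumed 1 to 3 replacements and assumed differences of 0.25 to 1.0 SD, an arm mean moves by 0.008 to 0.10 SD. This is a pilot that Section 4.2 describes as not powered to test efficacy. The case for changing the text is that the change is nearly free, closes a bias route, and keeps the retention denominators complete for planning the larger trial. If the database already releases the assignment only during the call, the bias route nearly closes, but the conflict between the two sections and the undefined set would remain.

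**What to change.** 1. **Section 7.2.** Make randomisation, meaning the assignment being drawn for that participant, the point after which a person is counted and not replaced. This matches Section 5.5.
2. **Section 9.3.** Define the intent-to-treat set as all randomised participants, analysed in the arm to which they were randomised.
3. **Section 6.3.** State that the assignment is drawn or released in the database only at the notification call, after eligibility has been re-confirmed.
4. **Reporting.** Give, by arm, the number randomised but not notified, with reasons.

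The cost is a few sentences and a change in the order of two database steps. The target of 60 and the sample size statement are unaffected.
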